10.5 Statistical analyses

The study population will be described including all documented variables (absolute and relative frequency, mean, median, quantiles, range etc.). The incidence of side effects of

the Adalimumab therapy will be described according to the physician's statement. The level of statistical significance is established to 5%, a multiple fit to a global level of significance is not planned.

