with the terms of the marketing authorization. Data on the safety and efficacy of Adalimumab will be collected from initial dosing and up to 60 months of therapy.

Well-designed observational cohort studies including a very strict study protocol and monitoring, are indispensable to complement the knowledge gained from randomized controlled trials with important real-life data. The gain in experience was recently demonstrated in the German register RABBIT in rheumatoid arthritis patients. RABBITT provided information that the majority of patients with various comorbidities, concomitant medications, dosing schemes, and disease states, who would not fulfill the inclusion criteria of a major trial, benefit from biologic therapy (14).

5. Study Objective

The primary objective of the non-investigational study (PMOS) is to demonstrate long-term efficacy and safety of Adalimumab in patients with Crohn's disease under routine conditions and to evaluate the proportion of patients achieving remission and the time to remission induction.

Secondary objectives include: Improvement/resolution of signs and symptoms of the acute Crohn's disease (CDAI –100), rate of adverse events, and long-term improvement of patients QOL.

Further, the observation study protocol enables physicians to characterize patients that fulfill criteria for Adalimumab treatment thus ensuring the requirements of reimbursement.

6. Investigational Plan

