7.1 Adverse Event Definition and Serious Adverse Event Categories

An adverse event (AE) is defined as any untoward medical occurrence in a patient, which does not necessarily have a causal relationship with their treatment. An adverse event can therefore be any unfavorable and unintended sign (including an abnormal laboratory finding), symptom, or disease temporally associated with the use of a medicinal product, whether or not the event is considered causally related to the use of the product.

Such an event can result from use of the drug as stipulated in the labeling, as well as from accidental or intentional overdose, drug abuse, or drug withdrawal. Any worsening of a pre-existing condition or illness is considered an adverse event.

If an adverse event meets any of the following criteria, it is considered a **serious adverse event (SAE):**

Death of Subject An event that results in the death of a subject.

Life-Threatening An event that, in the opinion of the investigator, would have resulted in immediate fatality if medical intervention had not been taken. This does not include an event that would have been fatal if it had occurred in a more severe form.

Hospitalization An event that results in an admission to the hospital for any length of time. This does not include an emergency room visit or admission to an outpatient facility.

Prolongation of Hospitalization An event that occurs while the study subject is hospitalized and prolongs the subject's hospital stay.

Congenital Anomaly An anomaly detected at or after birth, or any anomaly that results in fetal loss.

Persistent or Significant Disability/Incapacity An event that results in a condition that substantially interferes with the activities of daily living of a study subject. Disability is not intended to include experiences of relatively minor medical significance such as headache, nausea, vomiting, diarrhea, influenza, and accidental trauma (*e.g.*, sprained ankle).

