7.3 Relationship to Pharmaceutical Product

The physician will use the following definitions for any adverse event being collected as an endpoint/datapoint in the study and for all serious adverse events, to assess the relationship of the adverse event to the use of the pharmaceutical product:

Probably Related An adverse event has a strong temporal relationship to study drug or recurs on re-challenge and another etiology is unlikely or significantly less likely.

Possibly Related An adverse event has a strong temporal relationship to the study drug and an alternative etiology is equally or less likely compared to the potential relationship to study drug.

Probably Not Related An adverse event has little or no temporal relationship to the study drug and/or a more likely alternative etiology exists.

Not Related An adverse event is due to an underlying or concurrent illness or effect of another drug and is not related to the study drug (*e.g.*, has no temporal relationship to study drug or has a much more likely alternative etiology).

If an investigator's opinion of possibly, probably not, or not related to pharmaceutical product is given, an alternate etiology must be provided by the investigator for the adverse event.

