Each study center receives either online permission to a database or binders with a set of sheets for data collection, depending on the technical equipment of the centre. The required data should be entered in to the data sheets using the physicians' documentation. Any observation of an adverse event in the time period up-to 60 months, beginning with the initiation of HUMIRA® therapy, must be documented on the "Adverse Event Form", labeled 'Bericht über unerwünschte Ereignisse' and checked for severity. If the event fulfills the serious criterion (Serious Adverse Event) the "Adverse drug reaction report" form, labeled 'Bericht über unerwünschte Arzneimittelwirkungen' must be completed in addition.

10 Data Analysis Plans

All statistical analysis procedures are described in detail in a statistical analysis plan. This plan will be established by the biometric before the database will be opened for the first interims analysis, and signed by the sponsor, the principle investigator and the biometric.

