10.4 Biometric concept

The aims of the biometric concept for the statistical analysis include:

- Assessment of the safety of the Adalimumab therapy by evaluation and registration of side effects
- Assessment of the efficacy of the Adalimumab therapy by evaluating the proportion of patients achieving remission (remission as defined according to CDAI or HBI scores)
- Assessment of factors of influence to remission (logistic regression models), e.g. duration of therapy, concomitant medication in the medical history, extraintestinal manifestation, kind of Crohn's disease (fistula, stenoses)
- Assessment of the duration until remission
- Assessment of factors influencing time until remission (Cox regression models)
- Assessment of centre effects
- Subgroup analyses based on the results of the regressions analyses

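### The safety objective is the rate of all adverse events, but the only safety outcome named in Sections 10.4 and 10.5 is side effects as stated by the physician

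*Protocol*

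**What the plan says.** Section 5 gives the primary objective as "to demonstrate long-term efficacy and safety of Adalimumab in patients with Crohn's disease under routine conditions". Its secondary objectives include "rate of adverse events, and long-term improvement of patients QOL".

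Section 7.1 defines an adverse event broadly, "whether or not the event is considered causally related to the use of the product". Section 7.3 then gives physicians a four-level scale "to assess the relationship of the adverse event to the use of the pharmaceutical product". Section 9 sets the collection rule: "Any observation of an adverse event in the time period up-to 60 months, beginning with the initiation of HUMIRA® therapy, must be documented".

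Section 10.4 states the safety aim as "Assessment of the safety of the Adalimumab therapy by evaluation and registration of side effects". Section 10.5 says that the incidence of side effects of "the Adalimumab therapy will be described according to the physician's statement". The sentence before it plans a description of the study population that takes in every recorded variable, using counts, percentages and summary statistics. Adverse events and serious adverse events are on the follow-up data list in Section 6.5. The opening of Section 10 leaves the detail of the procedures to a statistical analysis plan, which is not at hand.

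**The concern.** The objective and the data collection concern adverse events whatever their cause. The analysis section names something narrower on its face: effects of the drug, as stated by the treating physician. Section 10 does not name all-cause adverse events or serious adverse events as an outcome in their own right.

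The difference matters because of the design. There is one arm and no blinding, and the physician who judges causality also chose the treatment. In a controlled trial, a difference between arms in all-cause events would show whether attribution had missed something. Here no such check exists, so the all-cause rate is the one figure that does not depend on the physician's opinion. If the attributed figure is the headline result, the safety objective is answered by judgement and not by observed events.

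There is also a second, weaker issue. The protocol expects heavy drop-out over five years, so an incidence means little until its denominator is known, and Section 10.5 gives none.

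**Working it through.** The protocol states no adverse event rate, safety precision target or share of related events, so there is no figure to reproduce. The check compares the sections and then works out what the protocol's own drop-out assumption implies.

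**1. Outcome in the objective against outcome in the analysis**

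| Place | Outcome | Depends on causality? |
|---|---|---|
| Section 5 | Rate of adverse events | No, by the definition in 7.1 |
| Section 9 | Every adverse event to month 60 | No |
| Section 10.4 | Side effects | Yes, on the ordinary meaning |
| Section 10.5, safety sentence | Side effects of the therapy, per the physician | Yes, on the ordinary meaning |
| Section 10.5, general sentence | All recorded variables, by frequency | No, but safety is not named |

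**2. Effect of attribution**

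Let s be the share of adverse events judged related, with s between 0 and 1. Then:

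attributed rate = s × all-cause rate

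The attributed rate can never exceed the all-cause rate. The protocol gives no value of s. An assumed range of 30% to 100% would give 0.3 to 1.0 times the all-cause rate, but nothing in the protocol supports a particular value. Only the direction is established.

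**3. Follow-up actually observed**

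Inputs: N = 2000 and annual drop-out d = 20% to 30% (Section 10.1); 60 months per patient (Section 6.4). Drop-out is taken as the end of observation at a constant hazard L = −ln(1 − d).

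- Patients remaining at month 60 = N(1 − d)^5: 2000 × 0.8^5 = 655; 2000 × 0.7^5 = 336.
- Patient-years = N(1 − exp(−5L))/L. With L = 0.2231 this is 6026; with L = 0.3567 it is 4665.
- Full follow-up is 2000 × 5 = 10,000 patient-years, so 60% to 47% is observed, a mean of 3.0 to 2.3 years per patient.

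**4. What a simple proportion would give, if one were used**

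For an assumed constant first-event hazard h that is independent of drop-out:

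- true 5-year risk = 1 − exp(−5h)
- crude proportion of all patients = h/(h + L) × (1 − exp(−5(h + L)))

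| h per 100 patient-years (assumed) | 5-year risk | Crude, 20% drop-out (ratio) | Crude, 30% drop-out (ratio) |
|---|---|---|---|
| 1 | 4.88% | 2.95% (0.605) | 2.29% (0.470) |
| 3 | 13.93% | 8.51% (0.611) | 6.64% (0.476) |
| 5 | 22.12% | 13.63% (0.616) | 10.69% (0.483) |
| 10 | 39.35% | 24.80% (0.630) | 19.67% (0.500) |

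The ratio is 0.60 to 0.63 at 20% drop-out and 0.47 to 0.50 at 30%. It hardly depends on the assumed hazard.

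Events divided by patient-years return the assumed hazard in every row. For h = 5 and 20% drop-out, 2000 × 0.1363 = 273 first events arise over 2000 × (1 − exp(−5 × 0.2731))/0.2731 = 5454 patient-years at risk, which is 5.0 per 100.

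**The case against.** The strongest reply is that the protocol does not exclude all-cause events. The general sentence in 10.5 covers every recorded variable, and adverse events are recorded. The list of aims in 10.4 is open-ended. The safety vocabulary is loose elsewhere: Section 7.5 uses severe where its subject is serious events, and Section 9 puts every serious adverse event, related or not, on a drug reaction form. Side effects may therefore simply mean adverse events, and the reference to the physician may mean only that events are described as reported. All of this is fair. A reader might infer that safety is analysed through attribution alone, and the text does not go that far. What stands is that the named safety outcome differs from the objective. If the wording is merely loose, it still needs correcting, because the author of the statistical analysis plan has to work from it.

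A second reply is that denominators, intervals and time windows belong in the statistical analysis plan. This also stands. Section 10.5 speaks of incidence without saying whether it is per patient or per patient-year, so the table above shows a risk and not a planned error.

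A reader might also infer that late events would drop out of the summary, because even the possibly related category requires that "An adverse event has a strong temporal relationship to the study drug and an alternative etiology is equally or less likely". The documents do not support this. The relationship is to the drug and not to the first dose, and Section 6.5 describes repeated dosing, so an event in a late year on treatment can still be close in time to a dose.

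**Conclusion.** The mismatch is real and of moderate weight. Sections 5, 7.1 and 9 concern all adverse events, while 10.4 and 10.5 name side effects by the physician's statement as the safety outcome. All-cause events are left, at most, to a general frequency description. Without a control group, the named outcome cannot be verified and can only be equal to or lower than the all-cause figure.

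It would be tempting to conclude that long-term harm will be understated by a known amount. The protocol does not support that. The loss through attribution has no numerical basis in it. The ratio of about 0.5 to 0.6 applies only if crude proportions of all 2000 patients are used and read as 5-year risks; it also assumes a constant hazard and drop-out unrelated to the event. Only the 60% to 47% of full follow-up comes from the protocol's own figures, with drop-out taken to end observation at a constant hazard.

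**What to change.** Amend 10.4 and 10.5 so that the main safety summary is all adverse events and all serious adverse events regardless of causality, as events per 100 patient-years of observation with 95% confidence intervals. State whether first events or all events are counted; if all, the interval should allow for several events in one patient. Show physician-attributed reactions as a secondary subset, naming the Section 7.3 categories that count as attributed.

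Limit any post-treatment rate to the time in which events are actually collected. Section 7.4 ends reporting of serious events at a set interval after the last dose, whereas Section 9 requires adverse events to be recorded up to 60 months from the start of therapy. These two passages must be reconciled before the denominator can be defined.

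The cost is a change of wording. Adverse events are already to be collected, so the main summary needs no new event data. The price is that reported rates may look somewhat less favourable than an attributed-only figure.
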